**Tables with Similar Format:**

**Table 105: Laboratory Summary Statistics by Time Point and Treatment Group for the Safety Population – Potassium (mmol/L)**

**Table 106: Laboratory Summary Statistics by Time Point and Treatment Group for the Safety Population – Bicarbonate (mg/dL)**

**Table 107: Laboratory Summary Statistics by Time Point and Treatment Group for the Safety Population – Glucose (mg/dL)**

**Table 108: Laboratory Summary Statistics by Time Point and Treatment Group for the Safety Population – Blood Urea Nitrogen (mg/dL)**

**Table 109: Laboratory Summary Statistics by Time Point and Treatment Group for the Safety Population – Creatinine (mg/dL)**

**Table 110: Laboratory Summary Statistics by Time Point and Treatment Group for the Safety Population – eGFR (mL/min/1.73m^2)**

**Tables with Similar Format (continued):**

**Table 111:** Laboratory Summary Statistics by Time Point and Treatment Group for the Safety Population – Calcium (mg/dL)

**Table 112:** Laboratory Summary Statistics by Time Point and Treatment Group for the Safety Population – Albumin (g/dL)

**Table 113:** Laboratory Summary Statistics by Time Point and Treatment Group for the Safety Population – Total Protein (g/dL)

**Table 114:** Laboratory Summary Statistics by Time Point and Treatment Group for the Safety Population – Alkaline Phosphatase (U/L)

**Table 115:** Laboratory Summary Statistics by Time Point and Treatment Group for the Safety Population – AST (U/L)

**Table 116:** Laboratory Summary Statistics by Time Point and Treatment Group for the Safety Population – ALT (U/L)

**Table 117:** Laboratory Summary Statistics by Time Point and Treatment Group for the Safety Population – Direct Bilirubin (mg/dL)

**Table 118:** Laboratory Summary Statistics by Time Point and Treatment Group for the Safety Population – Total Bilirubin (mg/dL)

**Table 119:** Laboratory Summary Statistics by Time Point and Treatment Group for the Safety Population – Cystatin-C (mg/L)

**Table 120: Clinically Significant Graded Chemistry Results by Maximum Severity Post-Baseline, Parameter, and Treatment Group for Participants in the Safety Population Enrolled Prior to Protocol v11.0**

[Implementation Note: Repeat for the following treatment groups: All Participants, SAR440894 0.3 mg/kg, SAR440894 1 mg/kg, SAR440894 3 mg/kg, SAR440894 10 mg/kg, SAR440894 20 mg/kg, and Placebo.

The table will include the following parameters: Sodium (High), Sodium (Low), Potassium (High), Potassium (Low), Bicarbonate (High), Bicarbonate (Low), Glucose High), Glucose (Low), Blood Urea Nitrogen, Creatinine, eGFR, Calcium (High), Calcium (Low), Albumin, Total Protein, Alkaline Phosphatase, AST, ALT, Direct Bilirubin, and Total Bilirubin.]

Parameter	Treatment Group	N	Mild / Grade 1		Moderate/ Grade 2		Severe/ Grade 3	
			n	%	n	%	n	%
Sodium (High)	All Participants	x	x	xx	x	xx	x	xx
	SAR440894 0.3 mg/kg							
	...							
	Placebo							
Sodium (Low)	All Participants							
	SAR440894 0.3 mg/kg							
	...							
	Placebo							
Potassium (High)	All Participants							
	SAR440894 0.3 mg/kg							
	...							
	Placebo							
...	...							

Notes: Participants are counted once per maximum severity among all clinically significant labs experienced at any time point post baseline, including unscheduled assessments. N = Number of participants in the Safety Population enrolled prior to Protocol v11.0 with available results post-baseline.

**Table 121: Clinically Significant Graded Chemistry Results by Maximum Severity Post-Baseline, Parameter, and Treatment Group for Participants in the Safety Population Enrolled Under Protocol v11.0**

[Implementation Note: Repeat for the following treatment groups: All Participants, SAR440894 0.3 mg/kg, SAR440894 1 mg/kg, SAR440894 3 mg/kg, SAR440894 10 mg/kg, SAR440894 20 mg/kg, and Placebo.

The table will include the following parameters: Sodium (High), Sodium (Low), Potassium (High), Potassium (Low), Bicarbonate (High), Bicarbonate (Low), Glucose High), Glucose (Low), Blood Urea Nitrogen, Creatinine, eGFR, Calcium (High), Calcium (Low), Albumin, Total Protein, Alkaline Phosphatase, AST, ALT, Direct Bilirubin, and Total Bilirubin.]

Parameter	Treatment Group	N	Mild / Grade 1		Moderate/ Grade 2		Severe/ Grade 3		Life-threatening/ Grade 4		Death/ Grade 5	
			n	%	n	%	n	%	n	%	n	%
Sodium (High)	All Participants	x	x	xx	x	xx	x	xx	x	xx	x	xx
	SAR440894 0.3 mg/kg											
	...											
	Placebo											
Sodium (Low)	All Participants											
	SAR440894 0.3 mg/kg											
	...											
	Placebo											
Potassium (High)	All Participants											
	SAR440894 0.3 mg/kg											
	...											
	Placebo											
...	...											

Notes: Participants are counted once per maximum severity among all clinically significant labs experienced at any time point post baseline, including unscheduled assessments. N = Number of participants in the Safety Population enrolled under Protocol v11.0 with available results post-baseline.

**Table 122: Other Clinically Significant Abnormal Chemistry Results by Maximum Severity Post-Baseline, Parameter, and Treatment Group for Participants in the Safety Population Enrolled Prior to Protocol v11.0**

[Implementation Note: Repeat for the following treatment groups: All Participants, SAR440894 0.3 mg/kg, SAR440894 1 mg/kg, SAR440894 3 mg/kg, SAR440894 10 mg/kg, SAR440894 20 mg/kg, and Placebo.

The table will include the following parameters: Cystatin-C.]

Parameter	Treatment Group	N	Within Normal Range		Outside Normal Range	
			n	%	n	%
Cystatin-C	All Participants	x	x	xx	x	xx
	SAR440894 0.3 mg/kg					
	...					
	Placebo					

Notes: Participants are counted once per maximum severity among all clinically significant labs experienced at any time point post baseline, including unscheduled assessments. N = Number of participants in the Safety Population enrolled prior to Protocol v11.0 with available results post-baseline.

**Table 123: Other Clinically Significant Abnormal Chemistry Results by Maximum Severity Post-Baseline, Parameter, and Treatment Group for Participants in the Safety Population Enrolled Under Protocol v11.0**

[Implementation Note: Repeat for the following treatment groups: All Participants, SAR440894 0.3 mg/kg, SAR440894 1 mg/kg, SAR440894 3 mg/kg, SAR440894 10 mg/kg, SAR440894 20 mg/kg, and Placebo.

The table will include the following parameters: Cystatin-C.]

Parameter	Treatment Group	N	Within Normal Range		Outside Normal Range	
			n	%	n	%
Cystatin-C	All Participants	x	x	xx	x	xx
	SAR440894 0.3 mg/kg					
	...					
	Placebo					

Notes: Participants are counted once per maximum severity among all clinically significant labs experienced at any time point post baseline, including unscheduled assessments. N = Number of participants in the Safety Population enrolled under Protocol v11.0 with available results post-baseline.

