For ALT/AST; subjects who screened prior to Protocol Version 11.0 were excluded if AST/ALT results were Grade 1 or higher at Screening. Subjects who screen with Protocol Version 11.0, AST/ALT is exclusionary if Screening results are  $1.5 \times$  ULN or if assessed as CS by the site PI.

\*\*Grade 1 or higher toxicity, see [Appendix C](#) and [Appendix D](#) for subjects who screened and enrolled prior to Protocol Version 11.0. Subjects who screen and enroll with Protocol Version 11.0, toxicity will be assessed with the NCI CTCAE, Version 5.0 – November 2017. Safety laboratory tests drawn on Day -1 or Screening if within 48 hours of planned dosing will serve as baseline values. Day -1 laboratory tests with a Grade 1 severity, other than those noted above, will not exclude subjects from participation.

\*\*\* All other abnormal laboratory values collected at Screening and on Day -1 will be exclusionary at the discretion of the PI.

22. Potassium, bicarbonate, or creatinine/eGFR\* results are Grade 1 or higher at either Screening or Day -1/Baseline visits.

\*For creatinine; subjects who screened prior to Protocol Version 11.0 were excluded if creatinine results were Grade 1 or higher. Subjects who screen with Protocol Version 11.0, creatinine is not an exclusionary criterion, instead subjects should have a calculated eGFR using Chronic Kidney Disease Epidemiology Collaboration Creatinine Equation (CKD-EPI) of  $\geq 90$  mL/min/1.73m^2 to be enrolled in the study.

23. Received an experimental agent (vaccine, drug, biologic, device, or medication) within 45 days or 5 half-lives (whichever is longer) before study product administration.\*

\*Prior participation at any time in noninvasive methodology trials in which no drugs were given is acceptable.

---

24. Is participating in or plans to participate in another clinical trial with an interventional agent that will be received during this trial.
25. Has donated more than 500 mL of blood or blood products\* within the month before Screening.  
\*Includes whole blood, red blood cells, platelets, plasma, or plasma derivatives.
26. Has a history of serologically-proven CHIKV exposure at any point, or positive anti-CHIKV antibodies (ie, positive IgM or IgG) at Screening.
27. Has received blood products within 120 days prior to Screening.

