#### **8.2 Specification of Safety Parameters**

Safety will be assessed by the frequency and severity of AEs and SAEs; the incidence and maximum intensity of AEs and SAEs, vital sign measurements, ECG findings, and clinically important changes in clinical laboratory values, defined as a change to a higher grade relative to baseline.

AEs and SAEs will be addressed as they are reported or identified by a staff member. Safety laboratory reports are reviewed as available, generally within 24 hours of sample collection.

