#### **3.2. Endpoints**

##### **3.2.1. Primary**

- Occurrence of adverse events (AEs) and serious adverse events (SAEs) following the start of study product administration through the final visit (Day 150 [ $\pm 7$ ]), or Early Termination (ET).
- The occurrence of clinically significant (CS) changes from baseline in vital signs and clinical safety laboratory values following administration of study product through final visit (Day 150 [ $\pm 7$ ]), or ET.
- The occurrence of CS changes in electrocardiogram (ECG) parameters post administration of study product through the final visit (Day 150 [ $\pm 7$ ]), or ET.

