## Chemistry

- Proportions of participants with mild, moderate, and severe results for any chemistry parameter will be presented for participants who enrolled prior to Protocol v11.0 in [Table 70](#) by treatment group, severity at baseline, time point, and severity across all graded chemistry parameters. Proportions of participants with results that are mild, moderate, severe, life-threatening, or result in death for any chemistry parameter will be presented for participants who enrolled under Protocol v11.0 in [Table 71](#) by treatment group, severity at baseline, time point, and severity across all graded chemistry parameters.
- Proportions of participants with graded abnormal results will be presented by treatment group, severity at baseline, time point, and severity separately for participants enrolled prior to Protocol v11.0 and for participants enrolled under Protocol v11.0 for chemistry parameters beginning in [Table 72](#) and continuing through [Table 101](#). Chemistry parameters with separate high and low toxicity ranges will be summarized by severity with high and low ranges indicated. The

proportions of participants with ONR results will be presented by treatment group, severity at baseline, time point, and severity for chemistry parameters that do not have toxicity grading ranges defined in **Table 102** and **Table 103**.

- Proportions of participants with graded CS chemistry results post-baseline will be presented by parameter, treatment group, and maximum severity of all CS results post-baseline for participants enrolled prior to Protocol v11.0 in **Table 120** and for participants enrolled under Protocol v11.0 in **Table 121**. The proportions of participants with CS ONR chemistry results post-baseline will also be presented by parameter, treatment group, and maximum severity of all CS results for parameters that do not have toxicity grading ranges defined in **Table 122** for participants enrolled prior to Protocol v11.0 and in **Table 123** for participants enrolled under Protocol v11.0.

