## 9.7. Vital Signs and Physical Evaluations

Vital signs will include systolic blood pressure, diastolic blood pressure, heart rate, respiratory rate, and temperature. Vital signs will be assessed according to the schedule detailed in [Section 4.1](#) and [Table 2](#). Baseline will be defined for vital sign assessments according to the definition given in [Section 3.3](#). Clinical significance for post-baseline vital signs will be determined by the site PI with consideration to persistence, association with clinical symptoms, and impact to participant safety. For participants who screened and enrolled prior to Protocol v11.0, clinically significant vital signs will be determined by a blinded review from the site PI of all vital sign AEs reported. For participants who screened and enrolled with Protocol v11.0, clinically significant vital signs will include all abnormal vital signs results reported as AEs.

Toxicity grading criteria for vital signs results can be found in [Table 5](#) and [Table 6](#) for participants who screened and enrolled prior to Protocol v11.0. Vital signs results post-dosing for participants who screened and enrolled with Protocol v11.0 will be graded according to NCI CTCAE, Version 5.0 – November 2017. The distribution of vital signs results will be presented by severity, treatment group, and time point.

The sort order for vital signs assessments will be as follows: SBP, DBP, heart rate, respiratory rate, and temperature.

- Proportions of participants with mild, moderate, and severe results for any vital sign assessment will be presented for participants who enrolled prior to Protocol v11.0 in [Table 202](#) by treatment group, time point, and maximum severity. Proportions of participants with results that are mild, moderate, severe, life-threatening, or result in death for any vital sign assessment will be presented for participants who enrolled under Protocol v11.0 in [Table 203](#) by treatment group, time point, and maximum severity.
- Proportions of participants with graded abnormal vital signs results will be presented by treatment group, time point, and maximum severity separately for participants enrolled prior to Protocol v11.0 and for participants enrolled under Protocol v11.0 for vital sign parameters beginning in [Table 204](#) through [Table 213](#). Vital sign parameters with separate high and low toxicity ranges will be summarized by maximum severity for both high and low ranges.

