Diastolic Blood Pressure	All Participants											
	SAR440894 0.3 mg/kg											
	...											
	Placebo											
...	...											

Notes: Participants are counted once per maximum severity among all clinically significant vital signs experienced at any time point post baseline, including unscheduled assessments. N = Number of participants in the Safety Population enrolled under Protocol v11.0 with available results post-baseline.

**Table 221: Summary of Post Dose ECG Change in Overall Interpretations from Baseline by Treatment Group and Time Point - Safety Population**

[Implementation Note: This table will include the following treatment groups: All Participants, SAR440894 0.3 mg/kg, SAR440894 1 mg/kg, SAR440894 3 mg/kg, SAR440894 10 mg/kg, SAR440894 20 mg/kg, Placebo.]

Treatment Group	N	Change from Baseline in ECG Interpretation					
		Normal at Both Times n (%)	Normal to Abnormal, NCS n (%)	Normal to Abnormal, CS n (%)	Abnormal, NCS at Both Times n (%)	Abnormal, NCS to Abnormal, CS n (%)	Abnormal, NCS to Normal n (%)
Day 1							
All Participants	x	x (x)	x (x)	x (x)	x (x)	x (x)	x (x)
SAR440894 0.3 mg/kg	x	x (x)	x (x)	x (x)	x (x)	x (x)	x (x)
...							
Placebo	x (x)	x (x)	x (x)	x (x)	x (x)	x (x)	x (x)
Day 4							
All Participants	x	x (x)	x (x)	x (x)	x (x)	x (x)	x (x)
SAR440894 0.3 mg/kg	x	x (x)	x (x)	x (x)	x (x)	x (x)	x (x)
...							
Placebo	x	x (x)	x (x)	x (x)	x (x)	x (x)	x (x)
Final Visit (Day 150)							
All Participants	x	x (x)	x (x)	x (x)	x (x)	x (x)	x (x)
SAR440894 0.3 mg/kg	x	x (x)	x (x)	x (x)	x (x)	x (x)	x (x)
...							
Placebo	x	x (x)	x (x)	x (x)	x (x)	x (x)	x (x)

Notes: N = Number of participants in the Safety Population with ECG measurements at the time points indicated.  
NCS = Not clinically significant, CS = Clinically significant.

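### The clinically significant (CS) laboratory tables ignore baseline, so no planned summary table reports the primary endpoint of CS laboratory changes from baseline

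*SAP*

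**What the plan says.** SAP section 3.2.1, in the same terms as Protocol section 3.3.1, makes this a primary endpoint: "The occurrence of clinically significant (CS) changes from baseline in vital signs and clinical safety laboratory values following administration of study product". Protocol section 8.2 lists among its safety measures "clinically important changes in clinical laboratory values, defined as a change to a higher grade relative to baseline".

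For the CS laboratory tables, SAP section 9.6 (Chemistry) says "Proportions of participants with graded CS chemistry results post-baseline will be presented by parameter, treatment group, and maximum severity of all CS results post-baseline". Hematology, coagulation and urinalysis follow the same pattern. The table footnote gives the counting rule: "Participants are counted once per maximum severity among all clinically significant labs experienced at any time point post baseline". The denominator in these shells is participants with post-baseline results; a baseline value is not required.

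A separate set of laboratory tables does use baseline: "Proportions of participants with graded abnormal results will be presented by treatment group, severity at baseline, time point, and severity separately". These are the shift tables (70-103, 124-145, 160-167, 173-194). They include every graded or out-of-range result, whether or not it was flagged CS.

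Eligibility leaves room for abnormal baselines. Protocol section 5.1.2, exclusion 21, says "Day -1 laboratory tests with a Grade 1 severity, other than those noted above, will not exclude subjects from participation".

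For vital signs, the footnote to Tables 219-220 is parallel: "Participants are counted once per maximum severity among all clinically significant vital signs experienced at any time point post baseline". SAP section 9.7, however, takes CS vital signs from results reported as adverse events (participants under v11.0) or from a blinded investigator review of vital-sign adverse events (participants before v11.0).

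**The concern.** The endpoint is a change, but the tables that appear meant to report it count a state. A participant who entered with an abnormality, still has it at the same grade, and has it flagged CS after dosing is tabulated as having had the event. The shift tables cannot correct this, because they do not separate CS from other results and the two sets of tables cannot be linked participant by participant. SAP section 15, which lists departures from the protocol, does not mention this one.

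What is at stake is the reported incidence of a primary safety endpoint in groups of six, where a single participant is visible. Urinalysis matters in particular: the nonclinical signals were renal inflammation in mice and raised urine protein or albumin ratios in primates (Protocol sections 2.1 and 2.3.1), and Tables 198-199 report urine protein under the same rule.

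**Working it through.** The plan states no figure to reproduce; the check is mainly a comparison of texts.

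**1. What each laboratory table conditions on**

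| Source | Limited to CS results? | Uses baseline? |
|---|---|---|
| Primary endpoint (SAP 3.2.1) | Yes | Yes |
| Shift tables 70-103, 124-145, 160-167, 173-194 | No | Yes |
| CS tables 120-123, 156-159, 171-172, 198-201 | Yes | No |

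No table has both properties. The Table 200 footnote also omits the limit to CS results that its companion shells carry.

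**2. Can the case arise?** Exclusion 21 allows screening hemoglobin within 0.5 g/dL of the lower limit of normal. For women, Appendix C puts that limit at 12.0 and Grade 1 at 11.0-11.9. The lowest admissible value is 12.0 - 0.5 = 11.5 g/dL, which is Grade 1. Suppose such a participant is at 11.5 on Day -1 and at 11.5 on Day 28, and the later result is flagged CS. Table 156 counts her as a Grade 1 CS hemoglobin result. The shift table (126) places her as mild at baseline and mild afterwards. Protocol section 8.2 would not describe this as a change. The shift shells themselves carry a mild baseline row.

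**3. Size of one such count.** Group sizes are 6 per dose and 5 x 2 = 10 pooled placebo.

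- Dose group: 1/6 = 16.7% (exact 95% CI 0.4% to 64%), against 0/6 = 0% (0% to 46%) if only worsening counts.
- Pooled placebo: 1/10 = 10%.
- The CS laboratory tables are split by enrollment before or under v11.0, so a stratum of k participants moves by 1/k; with k = 3, for example, 1/3 = 33%. The documents do not give the split.

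**4. Chance of at least one such count (illustration only).** The documents give no rate. Let q be the assumed probability that a participant has a CS post-baseline laboratory result no worse in grade than an abnormal baseline, on any parameter. The chance in n participants is 1 - (1 - q)^n.

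| q (assumed) | n = 6 | n = 10 | n = 30 active |
|---|---|---|---|
| 1% | 5.9% | 9.6% | 26.0% |
| 2% | 11.4% | 18.3% | 45.5% |
| 5% | 26.5% | 40.1% | 78.5% |

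The tables are by parameter, so the chance for any single row is smaller.

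**5. Vital signs.** Protocol section 8.1.1 does not treat a condition present at screening as an adverse event unless it worsens, so the CS vital-sign set passes through an indirect baseline filter. The filter is imperfect. It refers to screening and not to the last pre-dose value. SAP section 6.7 records that all abnormal vital signs were adverse events before v11.0. The eligibility limit for heart rate (45 bpm) admits values of 45-50 bpm, which Appendix C grades as mild bradycardia when baseline is below 60.

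**The case against.** The strongest reply is that an investigator is unlikely to accept an abnormality at entry and later flag the same grade as CS. Exclusion 21 leaves other abnormal laboratory values to the investigator's discretion, and exclusion 22 bars Grade 1 potassium and bicarbonate at either visit, with a creatinine or eGFR limit according to protocol version. Little information is lost, either: Listings 15-18 show grade, CS flag and change from baseline in one row, Tables 62-69 list all results with the CS flag for anyone with an abnormal value, and the study is descriptive with no hypothesis test. All of this stands. It limits the likely frequency, but it does not make the tables report the stated endpoint. No laboratory CS criterion in either document refers to baseline.

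A second reply is that Protocol section 8.2 speaks of clinically important changes, while the endpoint speaks of CS changes, which are an investigator's judgment. A reader might infer that 8.2 formally defines the endpoint; neither document says so. The mismatch rests first on the endpoint's own reference to baseline, and 8.2 supports that reading for laboratory values only.

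A reader might also infer that the vital-sign tables fail in the same way, or hold no baseline information. They do not support that. The rule in section 9.7, "Proportions of participants with graded abnormal vital signs results will be presented by treatment group, time point, and maximum severity", has shells (Tables 202-213) whose first time point is Baseline, so group-level baseline severity is visible. What is missing is a within-participant cross-tabulation.

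Finally, a strict higher-grade filter would lose real worsening. Grade 1 AST in Appendix C runs from 42 to 105 U/L, so a marked rise can stay within one grade. Excluding participants out of range at baseline would hide worsening of an already abnormal cystatin-C, the renal injury biomarker. This stands, and it is why the any-CS count should be kept.

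**Conclusion.** The point holds for laboratory values. The CS tables report any CS result after dosing, the endpoint is a CS change from baseline, and no planned summary table closes the gap. One unchanged abnormality flagged CS would turn 0/6 into 1/6 (17%) in a dose group, and could move a smaller version stratum further. This rests on an investigator flagging an unchanged abnormality as CS, and the documents give no basis for a rate. The share of participants who enter with a Grade 1 value should not be read as the number miscounted, because the later result must also be flagged CS. The effect is on the descriptive incidence of a primary endpoint; power and type I error are not involved.

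For vital signs the point is narrower: neither document defines a CS change from baseline, and the adverse-event route filters for it only indirectly.

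**What to change.** **Graded laboratory parameters (Tables 120-121, 156-157, 171-172, 198-199).** Keep the any-CS count. Add baseline severity rows as in Tables 70-101. Add a count of participants whose highest-grade CS result exceeds their own baseline grade for the same parameter and direction, with the denominator limited to those who have both values.

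**Ungraded laboratory parameters (Tables 122-123, 158-159, 200-201).** Show CS out-of-range results separately for participants in range and out of range at baseline, without excluding the latter. Align the Table 200 footnote with its companions.

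**Vital signs.** State in SAP section 9.7 how a CS change from baseline is derived, and cross-tabulate Tables 219-220 by baseline grade.

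**SAP text.** Define a CS laboratory change from baseline in section 3.3 or 9.6, and say that the any-CS count is a supplementary display.

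The cost is a few sentences of SAP text, revised shells and some programming. Baseline grade is already derived for the laboratory shift tables and for the Baseline rows of Tables 202-213. No new data collection is needed.
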